Based on this work, our primary hypothesis is that older adults will not achieve a state of heat balance (i.e., rate of heat loss balancing the rate of heat gain; thermal equilibrium) and therefore experience greater heat storage throughout the 9-hour simulated heatwave compared to the younger participants. Consequently, body core temperature will be greater in the older adults and between-group differences will be exacerbated as exposure progresses. We will also explore the secondary hypothesis that differences in body temperature will be paralleled by greater alterations in cardiovascular variables and circulatory and intracellular markers of acute inflammation and stress in the older adults.

Intervention 2: Our primary hypothesis is that body heat storage will be exacerbated in the older adults exposed to the cooling centre intervention upon return to the heat (hours 5-6) compared to the older adults from Intervention 1 who remained in the heat. Consequently, body core temperature will be comparable (statistically equivalent) between groups by the end of exposure (i.e., 9 hours, 3 hours after return to the heat). This is because body temperature is regulated through a negative feedback mechanism. Elevations in core and skin temperatures elicit proportional activation of cutaneous vasodilation and sweating to facilitate heat loss and stabilize body temperature. Thus, core and skin cooling will suppress heat loss and, upon return to a hot environment, heat will be rapidly gained until body temperature rises to an extent sufficient to activate heat loss and re-attain thermal equilibrium. We will also evaluate the secondary hypothesis

that, in parallel to body core temperature, any effect of cooling on cardiovascular responses and acute inflammation will be abated by the end of the heat event.

METHODS

Participants

A total of 20 young (age: 18-30 years) and 40 older (age: 64-80 years) adults will be recruited for the project. Young (n=20) and older (n=20) adults will be recruited for **Intervention 1** and a separate cohort of older adults (n=20) for **Intervention 2**. Details on the determination of the sample sizes for each intervention are provided below.

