Intervention 1: An *a priori* power analysis determined that a total sample size of 19 young and 19 older adults is required to detect a difference in the rate of whole-body heat storage between groups at the end of each calorimeter session (i.e., hours 3 and 9) with 80% statistical power. In lieu of clinically meaningful data (i.e., what would be considered a clinically meaningful change in whole-body heat storage), the standardized effect size (Cohen's $d = 1.06$) was calculated from the difference in the rate of body heat storage between young and older adults over the final 30-min of a 3-hour heat exposure (young: -2 [26] kJ/hour, older: 43 [54] kJ/hour) in our previous work (Kenny et al. *Temperature (Austin)*. 2016 31;4(1):79-88).

Intervention 2: An *a priori* power analysis determined that a total sample size of 18 older adults in each group is required to confirm whether between-group differences in rectal temperature are within upper and lower bounds of +0.3°C and -0.3°C, respectively, with 80% power. This corresponds to an effect size (Cohen's d) of 1.0, based on the pooled-standard deviation of 0.3°C. Equivalence bounds were chosen based on the typical day-to-day variation of body core temperature (Consolazio et al. *Physiological measurements of metabolic functions in man*. 1963:453-480) and suggested meaningful/detectable change in body core temperature in a recent study assessing the influence of personal cooling strategies on physiological strain in young adults (Morris et al. *Annals of Internal Medicine*. 2019;171(9):675-677). The standard deviation for the between group difference was determined from data from our laboratory demonstrating a 0.2°C (SD 0.3) difference in rectal temperature between young and older adults (Kenny et al.

Temperature (Austin). 2016;4(1):79-88) and a 0.0°C (SD 0.3) difference between older adults with and without type 2 diabetes (Poirier et al. *Temperature (Austin)*. 2020;7(3):263-269) during 3 hours of rest in the heat (44°C, 30% relative humidity).

Experimental Design

Pre-trial instructions

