Statistical analysis for **Intervention 1** will compare whole-body heat storage and the resultant progression of body temperature, cardiovascular and acute inflammatory responses between the young and older adults during the simulated heatwave. Whole-body heat storage (primary outcome), body temperature responses including rectal temperature (primary outcome) and mean skin temperature (secondary outcome), as well as cardiovascular responses (secondary outcomes) will be evaluated using linear mixed-effects models. Time will be modelled as a repeated within-subject fixed effect (two levels: 3 and 9 hours), and age-group (two levels: young and older adults) will be modelled as a between-subject fixed effect. Pre-heat exposure values of the outcome variable, participant sex, and self-reported weekly physical activity (min/week, as assessed via the GAQ) will be included as covariates. Circulating and intracellular markers of acute inflammation and stress (secondary outcomes) will be evaluated using a similar model but without the fixed effect of time (data was only collected at the end of exposure) and baseline values included as a covariate (where appropriate). Participant identification will be modeled as a random effect in all analyses. Akaike's information criterion will be used to determine random effect and variance/covariance structures.

Post hoc multiple comparisons will be made on model estimated marginal means. Given the small number of comparisons for each variable, multiplicity corrections will not be employed. Homoscedasticity will be evaluated for all models by visual assessment of residual plots. Approximate normal distribution of residuals will be assessed via visual inspection of histograms and Q-Q plots. Data will be log-transformed in the event that the distribution of residuals meaningfully deviates from normality. For all analyses, the level of significance will be set at $P < 0.050$. Descriptive statistics will be presented as means and standard deviations. Comparisons between groups and/or time-points will be presented as means and 95% confidence intervals [lower limit, upper limit].

Intervention 2

Statistical analysis for Intervention 2 will evaluate the acute and lasting impacts of the short-term cooling intervention (i.e., during cooling and following return to the heat, respectively) on physiological responses.

Cumulative heat storage (primary outcome)

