The analysis of secondary variables will focus on whether there was a lasting effect of cooling 3 hours following return to the heat. However, we will also perform tertiary exploratory analysis to evaluate whether the end-exposure responses are similar (equivalent) within pre-specified bounds. Describing clinically meaningful bounds in this context is complex since there is little research regarding how the risk of adverse health events changes with *acute* alterations in cardiovascular responses or inflammatory status during heat exposure (or cooling). For heart rate (± 5 beats/min) and rate pressure product (± 1500 beats/min), the equivalence bounds for these exploratory analyses will be based on meaningful/detectable differences employed in recent studies evaluating the efficacy

of personal cooling strategies in laboratory-based studies (Morris et al. *Annals of Internal Medicine*. 2019;171(9):675-677). For arterial blood pressure responses, we will consider ± 5 mm Hg an appropriate clinically meaningful bound, given the associated 9%, 13%, and 6% reduction in risk of myocardial infarction, stroke, and mortality (Psaty et al. *Arch Intern Med*. 2001;161(9):1183-1192). For the other variables, reasonable equivalence bounds are not forthcoming. We will therefore set the bounds for these outcomes at ± 1 SD of the between-group difference (based on our sample size determination).

For all models, participant identification will be modeled as a random effect and Akaike's information criterion will be used to determine random effects and variance/covariance structure. The level of significance will be set at $P < 0.050$. Descriptive statistics will be presented as mean (standard deviation). Both 90% confidence intervals and 95% confidence intervals will be computed to facilitate interpretation of the equivalence testing and null hypothesis significance testing (respectively).

As noted at the start of the document, the statistical analysis plan was submitted after cleaning and analysis of the full data set, but prior to unblinding of the data.

Delimitations and limitations

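### Does Intervention 1's figure of 19 per group for 80% power conflict with the uncorrected 0.05 tests in the analysis plan?

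*Combined protocol and SAP*

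**What the plan says.** Under Sample size calculations, Intervention 1, the requirement reads: "total sample size of 19 young and 19 older adults is required to detect a difference in the rate of whole-body heat storage". The effect size, d = 1.06, comes from an earlier 3-hour study: -2 (SD 26) kJ/hour in the young and 43 (SD 54) kJ/hour in the older adults. The timing and the power for this comparison are given as follows: "at the end of each calorimeter session (i.e., hours 3 and 9) with 80% statistical power". The paragraph gives no alpha, sidedness, test, dropout allowance or between-hour correlation. It does not say whether the 80% applies to each hour or to both together. The Participants section recruits 20 per group.

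The Statistical analysis plan for Intervention 1 fits a mixed model with age group and time (3 and 9 hours), adjusted for the pre-exposure value, sex and physical activity. It then states: "Post hoc multiple comparisons will be made on model estimated marginal means". On multiplicity: "Given the small number of comparisons for each variable, multiplicity corrections will not be employed". The sentence that begins "For all analyses, the level of significance will be set at" fixes that level at 0.050.

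The primary hypothesis is that older adults will "experience greater heat storage throughout the 9-hour simulated heatwave compared to the younger participants".

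**The concern.** A sample size should be traceable to the test it supports. Read plainly, the analysis section offers one contrast per hour at an uncorrected 0.05, and 19 is three to four per group more than that contrast needs. A two-sided 0.025 per hour gives 19 exactly, which suggests that the calculation assumed an alpha split that the analysis section rules out. The paragraph for Intervention 2 sharpens the suspicion. There, "total sample size of 18 older adults in each group is required" does reproduce for a single equivalence contrast at 0.05, so the gap for Intervention 1 is not just a matter of software or rounding.

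Two things would be at stake if the documents truly conflicted. The stated power of a primary outcome would belong to a different test from the one planned. A reader would also not know whether a difference at one hour, or only at both, supports the hypothesis. The second point matters more because "the statistical analysis plan was submitted after cleaning and analysis of the full data set, but prior to unblinding of the data".

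**Working it through.** **Inputs.** Means, SDs, d = 1.06, 80% power and hours 3 and 9 come from Sample size calculations, Intervention 1. The 0.050 level and the absence of correction come from the Statistical analysis plan, Intervention 1. Two-sided testing is inferred from the 95% confidence intervals promised there. The between-hour correlation is not given, so 0 to 0.8 is assumed and shown as a range.

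**Effect size.** d = 45 / √((26² + 54²)/2) = 45 / √1796 = 45 / 42.4 = 1.062. This agrees with the stated 1.06.

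**One hour, two-sided 0.05.** The power is that of a two-sample t-test with noncentrality d√(n/2) and 2n - 2 degrees of freedom.

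| n per group | noncentrality | critical t | power |
|---|---|---|---|
| 14 | 2.804 | 2.056 | 77.0% |
| 15 | 2.903 | 2.048 | 80.0% |
| 16 | 2.998 | 2.042 | 82.7% |
| 19 | 3.267 | 2.028 | 88.9% |
| 20 | 3.352 | 2.024 | 90.4% |

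Welch's test with SDs 26 and 54 (simulated) gives 78.9% at 15, 81.7% at 16, about 88% at 19 and 89.9% at 20. Removing 3 degrees of freedom for covariates gives 88.7% at 19. On this reading 15 or 16 per group suffice, and 19 is not reproduced.

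**Two-sided 0.025 per hour.** 18 per group give 79.4% and 19 give 81.9%. The figure 19 is reproduced, but only with an alpha split that the analysis section declines.

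**Difference required at both hours, each at 0.05.** With independent hours, joint power at 19 is 0.8886² = 0.790. Simulated joint power for other correlations:

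| n per group | corr. 0 | 0.3 | 0.5 | 0.8 |
|---|---|---|---|---|
| 18 | 76% | 77% | 79% | 82% |
| 19 | 79% | 80% | 81% | 84% |
| 20 | 82% | 83% | 84% | 86% |

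For correlations of about 0.3 to 0.5, 18 fall just short of 80% and 19 reach it. No alpha split is needed.

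**Dropout allowance.** 15 / 0.80 = 18.75 and 16 / 0.85 = 18.8. Both round up to 19.

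**Power with the 20 per group recruited.**
- Per hour at 0.05: about 90%.
- Per hour at 0.025: 84.1%.
- Both hours at 0.05: 82% to 86%. The least favourable case, Welch with independent hours, gives 0.899² = 0.808, or about 81%.
- If 15-20% were lost, 17 or 16 per group would remain, with 85.0% or 82.7% per hour.

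**Intervention 2, for comparison.** Two one-sided tests at 0.05, bounds of ±1 SD and a true difference of zero give 77% at 17 and 80% at 18. The stated 18 is reproduced.

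**The case for a change.** The best case for a change concerns the success rule more than the number 19. No section says whether the group effect, either hour or both hours would support the heat-storage hypothesis, and the false-positive rate depends on that. At 20 per group and correlations of 0 to 0.8, it is about 8-10% if either hour counts without a gate and about 2% or less if both are required. Each route to 19 also rests on something the documents leave unsaid, and a few added words would cost nothing.

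Part of this stands. The paragraph is incomplete, and a statement of alpha, sidedness, test and joint or per-hour power would help readers. The both-hours reading is also not a perfect match: with independent hours 20 would be needed, and at a correlation of 0.8 about 18 would do.

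The charge of inconsistency does not stand. The sample-size sentence names the end of each session, and the hypothesis speaks of the whole exposure. Detection at both hours is a natural reading of those words, and it leaves the two sections in agreement. The error-rate argument is a separate multiplicity question. The plan declines correction openly and gives its reason, which is a trade-off it may make. Restating the power as 88-89% would presume the single-hour reading, and that figure is an unadjusted approximation to a covariate-adjusted mixed model.

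**Conclusion.** The arithmetic behind the concern is right: 19 per group does not follow from a single-hour, uncorrected 0.05 contrast, which needs 15 or 16. The documents do not show that 19 is wrong, because it fits a both-hours requirement with moderate correlation (about 80-81%) and also a 15-20% dropout allowance. The gap is one of reporting, and it errs on the safe side. With 20 per group, power at the assumed effect runs from about 81% in the least favourable of these readings to about 90%.

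No change follows. Rewriting the calculation would add no participants, alter no model and change no result. An alpha split or a gate would replace a trade-off that the plan has disclosed. Analysts can report both hourly contrasts with their 95% intervals as planned, and readers can see whether the difference appears at one hour or both.

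This rests on d = 1.06 applying at both hours, two-sided testing, unadjusted t or Welch comparisons standing in for the mixed model, and assumed correlations of 0 to 0.8. Losses beyond the one spare participant per group, combined with a both-hours requirement and low correlation, would take power a little below 80%.

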The primary aim of the study is to assess differences in body temperature regulation between young and older adults (Intervention 1) and the efficacy of a cooling centre intervention for limiting hyperthermia in the elderly (Intervention 2) during a 9-hour simulated extreme heat event. Body temperature regulation will be quantified as between-group differences in whole-body cumulative heat storage (i.e., the total amount of heat stored in the body) and body core temperature (rectal temperature, surrogate measure of body heat content) in each intervention.

Whole-body evaporative and dry heat loss will be continuously measured during the first and final 3 hours of exposure via the Snellen air calorimeter, which provides the only standard measure of these metrics. Calorimeter inflow and outflow values of absolute humidity and air temperature will be measured at 8 second intervals using high precision dew point hygrometry (Model 373H, RH Systems) and resistance temperature detectors (Black Stack model 1560, Hart Electronics), respectively. Air mass flow, equivalent to <0.3 m/s where the participant is seated, will be determined via differential thermometry over a known heat source in the effluent air stream. All data will be displayed and recorded on a personal computer with LabVIEW software (Version 7.0, National Instruments). Heat loss via sweat evaporation will be then determined using the outflow–inflow difference in absolute humidity, multiplied by air mass flow and the latent heat of vaporization of sweat (2427 J/g). Dry heat loss will be similarly derived from the outflow–inflow air temperature difference and specific heat capacity of air (1005 J/kg/°C). Ambient temperature (40°C) will be greater than that of the skin (~35-36°C), meaning that a negative dry heat loss will be measured. Dry heat exchange was therefore expressed as a dry heat gain.

Metabolic energy expenditure will be determined using indirect calorimetry. Expired oxygen (O₂) and carbon dioxide (CO₂) content will be measured with electrochemical gas analysers (AMETEK model S-3A/1 and CD 3A, Applied Electrochemistry) from air drawn from a 6 L fluted mixing box located within the calorimeter. Expelled air will be recycled back into the chamber to account for respiratory heat exchange. The gas analyzers and

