turbine ventilometer will be calibrated ~30 min prior to each 3-hour calorimetry measurement period. Endogenous metabolic heat production will be assumed to be equivalent to metabolic energy expenditure since no external work will be performed. Cumulative body heat storage will be evaluated as the temporal summation of total heat gain (heat production + dry heat gain) and evaporative heat loss.

Rectal temperature will be monitored using a general-purpose thermocouple temperature probe (Mon-a-therm General Purpose Temperature Probe, Mallinckrodt Medical Inc.) inserted ~12 cm past the anal sphincter with data collected in 15-s intervals using LabVIEW software (Version 7.0, National Instruments).

Secondary Measures

The secondary aim of the project is to evaluate the extent to which age-related alterations in body temperature regulation (Intervention 1) and short-term ambient cooling (Intervention 2) are associated with alterations in physiological responses that can contribute to dysfunction and injury during a prolonged extreme heat event (Meade et al. *Environ Int.* 2020;144:105909). These include whole-body mean skin temperature and clinically relevant cardiovascular responses, as well as circulating and intracellular markers of inflammation and stress.

Mean skin temperature

Skin temperature will be assessed every minute using surface temperature monitors (DS1922L Thermochron, OnSolution Pty Ltd) affixed to 8 body regions, using double-sided adhesives and medical tape, as described in ISO 9886:2004. Mean skin temperature will then be calculated using the provided weightings: forehead (7%), right scapula (17.5%), upper left chest (17.5%), upper right arm (7%), right forearm (7%), left hand (5%), right anterior thigh (19%) and left calf (20%).

Cardiovascular measurements

Electrocardiogram data from Holter monitor (Philips DigiTrak XT Holter Monitor, Philips) will be downloaded and analysed using Philips Zymed Software (Philips Zymed Version 3.0, Andover, MA). R-R interval data will be extracted from the ECG tracing (3 channel at

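### Intervention 1: the stated 80% power is for the end-of-session rate of heat storage, not the declared cumulative outcome, and the heat-balance clause of the primary hypothesis has no planned comparison with zero

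*Combined protocol and SAP*

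**What the plan says.** Four parts of the combined protocol and SAP bear on heat storage in Intervention 1.

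- **Hypotheses, Intervention 1.** The primary hypothesis begins that "older adults will not achieve a state of heat balance (i.e., rate of heat loss balancing the rate of heat gain; thermal equilibrium" and goes on to predict, as a consequence, greater storage than in the young group.
- **Sample size calculations, Intervention 1.** The calculation is to "detect a difference in the rate of whole-body heat storage between groups at the end of each calorimeter session (i.e., hours 3 and 9". The effect size comes from rates in kJ/hour "over the final 30-min of a 3-hour heat exposure" in earlier work: young -2 (SD 26), older 43 (SD 54).
- **Measurements, Primary Outcome measures.** The declared quantity, in each intervention, is "between-group differences in whole-body cumulative heat storage (i.e., the total amount of heat stored in the body", alongside rectal temperature. Its derivation is given as "Cumulative body heat storage will be evaluated as the temporal summation of total heat gain" and evaporative loss. No end-of-session rate or averaging window is defined as an outcome.
- **Statistical analysis plan, Intervention 1.** The outcomes are "Whole-body heat storage (primary outcome), body temperature responses including rectal temperature (primary outcome", followed by the secondary ones. "Time will be modelled as a repeated within-subject fixed effect (two levels: 3 and 9 hours". The covariates are "Pre-heat exposure values of the outcome variable, participant sex, and self-reported weekly physical activity". Results are compared between groups and/or time-points.

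The SAP for Intervention 2, by contrast, states that its storage outcome is cumulative and gives the 3-hour window.

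**The concern.** A rate at the end of a session and a total over the session are different quantities with different variability. The document powers one, declares the other, and models an outcome that could be either. A reader could take the 80% as applying to the declared outcome, and the choice of confirmatory heat-storage quantity stays open. That matters more here because the SAP says it was submitted after cleaning and analysis of the full data set, though before unblinding.

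The heat-balance clause is a second gap. Whether older adults reach balance is a question about their own rate relative to zero. A comparison with the young group, or between hours 3 and 9, answers a different question.

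Third, the covariate rule asks for a pre-heat value of the outcome. Rectal temperature, skin temperature and the cardiovascular measures can have one. Heat storage cannot, because the calorimeter sits in the ~40°C chamber and measurement starts on entry. The model cannot be fitted as written for this primary outcome.

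**Working it through.** **Inputs.** Rates of -2 (SD 26) and 43 (SD 54) kJ/h, 19 per group and 80% power come from Sample size calculations. Recruitment of 20 per group comes from Participants. The 0.05 level comes from the SAP. Two-sided tests are assumed. Covariates and dropout are ignored.

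**1. The plan's own figure.** Pooled SD = √((26² + 54²)/2) = 42.4, so d = 45/42.4 = 1.06, as stated. Power is from the two-sample t-test with df = 2n - 2 and noncentrality d√(n/2):

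| n per group | two-sided 0.05 | two-sided 0.025 |
|---|---|---|
| 15 | 80.0% | 70.2% |
| 18 | 87.1% | 79.4% |
| 19 | 88.9% | 81.9% |
| 20 | 90.4% | 84.1% |

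The paragraph states no alpha. Its 19 for 80% is reproduced exactly at 0.025, which would be 0.05 split over hours 3 and 9, but that split is an inference. At 0.05, 15 suffice. A normal approximation at 0.05 also gives 19, but for 90% power, which is not what is stated. All of these figures concern the rate.

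**2. Cumulative storage.** The documents give no SD for it. Their only figure is about 80% greater storage in the earlier study (Hypotheses), which cannot be standardized. With n = 20 per group at two-sided 0.05, over an assumed range of d:

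| d | 0.5 | 0.6 | 0.8 | 0.9 | 1.0 | 1.2 |
|---|---|---|---|---|---|---|
| power | 34% | 46% | 69% | 79% | 87% | 96% |

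The smallest d with 80% power is about 0.91 (1.01 at 0.025).

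**3. The two readings of the SAP.** If it models the rate, power and model agree, but both depart from the declared outcome. If it models the sum, model and declared outcome agree, but the stated power does not apply. Neither reading reconciles all three sections.

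**4. Heat balance.**
- The young-older difference of 45 kJ/h has SE = √(26²/20 + 54²/20) = 13.4, Welch df 27.4, and a 95% CI of about 18 to 72. The same 45 results from 43 against -2 (older group out of balance) or from 0 against -45 (older group in balance).
- A positive 3-hour sum does not settle it either: heat stored early leaves a positive total even if the rate has reached zero by hour 3.
- A direct estimate would be informative at the plan's own figures. For the older group, half-width = 2.093 × 54/√20 = 25.3, giving 43 ± 25.3, or about 18 to 68 kJ/h. For the young group, 2.093 × 26/√20 = 12.2, giving about -14 to 10 kJ/h.
- Power of a one-sample t-test against 0 at 43/54 = 0.796 and n = 20 is about 92% at two-sided 0.05. At half that mean (21.5 kJ/h) it is about 39%.

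**5. Covariate.** The procedures describe no calorimetry before the participant enters the heated chamber, and heat exchange is measured only in the first and final 3 hours of exposure.

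**The case against.** The strongest reply is that the sample size paragraph is open about what it powers: it says rate, gives kJ/hour and names hours 3 and 9, which match the SAP's time levels. On that reading the discrepancy lies only in the Measurements section. This is fair, and it shows that the power statement is correct for the rate. It does not remove the mismatch with the declared outcome.

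On heat balance, the planned analysis is not limited to between-group contrasts. It includes time-point comparisons and would produce marginal means by group and time. If the modelled outcome is the rate, the older group's mean rate comes straight from the model. What is missing is then only the interval against zero and the statement that it will be read that way. If the outcome is the sum, the rate itself is missing.

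It can also be said that non-balance is the rationale for a between-group prediction, and that the primary aim is stated as between-group differences. That is true of the second clause. The first clause is still written as part of the primary hypothesis.

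The illustrative figures also have limits. The source data are from a 3-hour exposure that the Intervention 2 sample size paragraph appears to place at 44°C and 30% humidity, and the Hypotheses section calls its older group middle-aged-to-older. They may not transfer to ~40°C and ~10-15% humidity, to ages 64-80, or to hour 9.

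**Conclusion.** The point holds and should be fixed. The 80% belongs to the end-of-session rate, the declared outcome is cumulative storage, and the SAP names neither. No comparison of a group's rate with zero is specified for the heat-balance clause. The pre-heat covariate cannot be applied to heat storage; this is a drafting slip from one sentence covering many outcomes.

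Two stronger readings are not supported. A reader might infer that the trial is underpowered for cumulative storage. The documents give no SD for it, so power is unknown: adequate if d is about 0.91 or more at two-sided 0.05, inadequate below that. A reader might also infer that Intervention 1 cannot address its primary hypothesis. The declared outcomes do address the greater-storage and core-temperature clauses, and only the heat-balance clause lacks a specified analysis.

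The 18 to 68 kJ/h interval and the 92% power (39% at half the mean) are illustrations that rest on the earlier study's mean and SD. The documents give no figures for hour 9.

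**What to change.** 1. Name the quantities in the Primary Outcome section and the Intervention 1 SAP. Give cumulative storage as separate 3-hour sums for hours 1-3 and the final 3 hours, since hours 4-6 are spent outside the calorimeter. Give the end-of-session rate at hours 3 and 9 over a stated window, for example the final 30 min used for the effect size. Retain the between-group rate comparison that the sample size supports, and state that the 80% does not extend to the sums.
2. For the heat-balance clause, report the older group's model-estimated end-of-session rate at hours 3 and 9 with a 95% CI against 0 kJ/h, and the young group's likewise. State that an interval including 0 does not prove balance.
3. For heat storage, drop the pre-heat covariate and keep sex and physical activity.
4. Report rate and cumulative results whichever way they fall, and date the clarification relative to unblinding.

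The cost is some wording and a few added estimates from calorimetry already recorded continuously; no new participants or measurements are needed. The downside is slightly more analysis, and a cumulative outcome that openly carries no stated power.
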